14.3.7.1 Primary estimand for the continuous key secondary endpoints: 'composite'

The primary estimand for the continuous key secondary endpoints will be:

- Treatment difference in change from baseline to Week 16 in SCORAD and DLQI, respectively, achieved without rescue medication, regardless of discontinuation of IMP.

Primary analysis for the primary estimand - continuous key secondary endpoints

Data retrieved at Week 16 for subjects who have permanently discontinued IMP prior to Week 16 will be included in the analysis. Subjects who prior to the Week 16 visit have received rescue medication will be considered non-responders by using worst observation carried forward (including the baseline value).

Missing Week 16 data among subjects who did not use rescue medication will be imputed using multiple imputations (100 copies of the dataset, seed=16201343) assuming missing at random within arms (based on sequential use of an ANCOVA model for Weeks 2, 4, 6, ... and 16). The stepwise imputation model will be estimated based on available data from all subjects but excluding individual subject data captured after initiation of rescue medication or permanent discontinuation of IMP. For each of the 100 imputed datasets, the continuous secondary endpoint will be analysed using an ANCOVA model with effects of treatment, baseline disease severity (IGA 3 or 4), and baseline value. The estimates and standard errors from the 100 analyses will be combined using Rubin's rule to form a unique point estimate and standard error.

Sensitivity analysis for primary estimand - continuous key secondary endpoints

A tipping point analysis using multiple imputations will be performed with the purpose to assess the robustness of results of the primary analysis for the primary estimand with respect to the missing at random assumption regarding missing Week 16 data. The tipping analysis will assess how severe the departure from the missing at random assumption in the tralokinumab arm must be in order to impact the results.

The tipping point analysis will be performed using the missing at random imputed Week 16 data from primary analysis of the primary estimand. For each of the 100 already imputed datasets from the primary analysis, Δ will be added to the imputed values for subjects in the tralokinumab arm ($\Delta = 0$ implies missing at random) and thereby the imputed values will be 'shifted' by Δ . Each of the 100 modified imputed datasets will then be analysed in the same way as for the primary analysis for the primary estimand. The tipping point is then found as

the value of Δ which causes the 95% CI to change from excluding 0 to including 0 and will be judged from a clinical point of view.

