14.3.6.1 Primary estimand: ‘composite’

The primary estimand for the primary endpoints will be:

- Treatment difference in response rates of IGA 0/1 and EASI75 after 16 weeks achieved without rescue medication, regardless of treatment discontinuation.

The primary estimand assesses the expected difference in response rates (defined as response obtained without initiation of any rescue medication) after 16 weeks, resulting from initiation

of a treatment regimen with tralokinumab+TCS compared to a treatment regimen with placebo+TCS.

Primary analysis for the primary estimand

Data retrieved at Week 16 for subjects who have permanently discontinued IMP prior to Week 16 will be included in the analysis. Subjects who prior to the Week 16 visit have received rescue medication will be considered non-responders, reflecting an assumption that initiation of rescue medication indicates failure of the randomised treatment to achieve response, and that a (possible) observed positive response after initiation of rescue medication is not attributable to the randomised treatment. Missing data for subjects who do not attend the Week 16 visit and where rescue medication has not been used prior to Week 16, will be imputed as non-responders.

The difference in response rates between treatment groups will be calculated by the Mantel-Haenszel method stratified by baseline disease severity (IGA 3 or 4). The treatment difference and the corresponding 95% CI will be presented.

Sensitivity analysis

The purpose of the analysis is to assess the robustness of results of the primary analysis with respect to the retrieved data at Week 16.

All subjects who have permanently discontinued IMP prior to Week 16 will be imputed as non-responders, even if no rescue medication has been used. This is to reflect a situation where retrieved efficacy data and concomitant medications could be registered less accurately for subjects who have discontinued treatment. The same Mantel-Haenszel method as used for the primary analysis will be applied including stratification by baseline disease severity.

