14.3.6.2 Secondary estimand: ‘treatment policy’

The secondary estimand for the primary endpoints will be:

- Treatment difference in response rates of IGA 0/1 and EASI75 after 16 weeks regardless of rescue medication and discontinuation of IMP.

The secondary estimand assesses the average difference in response rates, resulting from initiation of a treatment regimen with tralokinumab+TCS and additional rescue medication as compared to a treatment regimen with placebo+TCS and additional rescue medication.

Primary analysis for the secondary estimand

All data used as observed at Week 16 regardless of rescue medication and discontinuation of IMP, thus data retrieved at Week 16 for subjects who have permanently discontinued treatment prior to Week 16 will be included in the analysis.

IGA 0/1 responder imputation

Imputation of missing binary IGA 0/1 data at Week 16 will be done using multiple imputations of the underlying 5-point IGA values within the 4 groups defined according to randomised treatment arm and whether or not subjects have permanently discontinued IMP prior to Week 16 assuming that data is missing at random within each arm. Within a given treatment arm, retrieved data from discontinued subjects will be used to impute missing data for other discontinued subjects. Similarly, the available data from not discontinued subjects will be used to impute data for such subjects where the Week 16 value is missing.

1. In each group, intermittent missing values will be imputed using last observation carried forward (LOCF) to obtain a monotone missing data pattern.
2. An ordinal logistic regression model assuming proportional odds will be fitted to the IGA value at Week 2. The model will include effect of baseline disease severity (IGA 3 or 4) as factor. The estimated parameters, and their variances, will be used to impute missing IGA values at Week 2. 100 copies of the dataset will be generated (seed=16201343).
3. For each of the 100 copies of the dataset, missing values at Week 4 will be imputed in the same way as for Week 2. The imputations will be based on a proportional odds logistic regression model with effects of baseline disease severity (IGA 3 or 4) together with the IGA value at Week 2 as factors. The estimated parameters, and their variances, will be used to impute missing values at Week 4.

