4. This stepwise procedure will then be repeated sequentially for Weeks 6, 8, 10, 12, 14, and 16 with the modification that only the IGA values from the 2 preceding visits will be included as factors in addition to baseline disease severity. The missing binary IGA 0/1 response at Week 16 will be derived from the corresponding underlying imputed IGA value.

For not discontinued subjects, the stepwise multiple imputations procedure will be conducted as described above.

For discontinued subjects, it is expected that the number of subjects with retrieved data at Week 16 will be too small to facilitate the same imputation model as mentioned above. Consequently, an imputation model with only baseline effects (IGA as a factor) will be

applied for discontinued subjects. Some factors may have to be omitted, depending on the observed data, e.g. if retrieved subjects all have the same baseline severity.

EASI75 responder imputation

Imputation of missing binary EASI75 data at Week 16 will be done using multiple imputations of the underlying 72-point EASI values within the 4 groups defined according to randomised treatment arm and whether or not subjects have permanently discontinued IMP prior to Week 16 assuming that data is missing at random within each arm. Within a given treatment arm, retrieved data from discontinued subjects will be used to impute missing data for other discontinued subjects. Similarly, the available data from not discontinued subjects will be used to impute data for such subjects where the Week 16 value is missing.

1. Intermittent missing values will be imputed in each group using a Markov Chain Monte Carlo method to obtain a monotone missing data pattern and 100 copies of the dataset will be generated (seed=11101343).
2. For each of the 100 copies of the dataset, an ANCOVA model will be fitted to the EASI value at Week 2. The model will include effects of baseline EASI as a covariate, and baseline disease severity (IGA 3 or 4) as factor. The estimated parameters, and their variances, will be used to impute missing EASI values at Week 2 (seed=16201343).

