14.3.7.2 Secondary estimand for the continuous key secondary endpoints: 'hypothetical'

The secondary estimand for the continuous secondary endpoints will be:

- Treatment difference in change from baseline to Week 16 in SCORAD and DLQI, respectively, if all subjects adhered to the treatment regimen in the sense that they did not discontinue IMP permanently and no rescue medication was made available before Week 16.

The secondary estimand assesses the expected benefit when adhering to the treatment regimen tralokinumab+TCS with no rescue medication as compared to a treatment regimen with placebo+TCS with no rescue medication.

Primary analysis for the secondary estimand - continuous key secondary endpoints

Data collected after permanent discontinuation of IMP or after initiation of rescue medication will not be included in the analysis. For subjects without any post-baseline data, the baseline value will be carried forward as the first post-baseline assessment, corresponding to imputing a change of 0 at the first post-baseline assessment. This is to ensure that all subjects will be included in the analysis. The endpoints will be analysed using a repeated measurements model on the post-baseline responses up to Week 16 with an unstructured covariance matrix, Kenward-Roger approximation to estimate denominator degrees of freedom, and the mean modelled as follows (shown for change from baseline in SCORAD):

Change from baseline in SCORAD

= treatment \times visit + baseline SCORAD \times visit + baseline IGA

This model assumes that data is missing at random within each treatment arm. The estimates will be presented with 95% CI at each visit. The primary comparison between tralokinumab+TCS and placebo+TCS will be at Week 16.

Sensitivity analysis for secondary estimand - continuous key secondary endpoints

Rather than assuming that observations are missing at random within each treatment arm it is assumed that missing data from subjects who discontinue IMP/receive rescue medication in the tralokinumab+TCS arm will resemble data from subjects from the placebo+TCS arm who do not discontinue IMP/receive rescue medication.

Imputation of missing data at Week 16 will be done using a pattern mixture model where missing data in the tralokinumab+TCS arm as well as the placebo+TCS arm will be imputed from the placebo+TCS arm (using multiple imputations in a so-called copy-reference approach).

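### SCORAD and DLQI: the primary estimand disregards IMP discontinuation, but unrescued discontinuers with no Week 16 value are imputed as if still on IMP

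*Protocol*

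**What the plan says.** Protocol 14.3.7.1 sets the primary estimand for the two continuous key secondary endpoints as the difference in change to Week 16 "achieved without rescue medication, regardless of discontinuation of IMP". Three rules implement it:

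- Discontinued subjects who return at Week 16 contribute their observed value.
- Subjects rescued before Week 16 receive their worst observation, baseline included.
- All other subjects without a Week 16 value are multiply imputed, assuming data are missing at random (MAR) within arm. The model is fitted "excluding individual subject data captured after initiation of rescue medication or permanent discontinuation of IMP". Discontinued subjects have no stratum of their own.

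Section 14.3.7.2 applies the same exclusion to the hypothetical estimand: "Data collected after permanent discontinuation of IMP or after initiation of rescue medication will not be included in the analysis". Its sensitivity analysis is a copy-reference procedure in which "missing data in the tralokinumab+TCS arm as well as the placebo+TCS arm will be imputed from the placebo+TCS arm".

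The binary endpoints are treated differently. Under the composite estimand (14.3.6.1), subjects who miss Week 16 "where rescue medication has not been used prior to Week 16, will be imputed as non-responders". Under treatment policy (14.3.6.2), imputation is by arm and discontinuation status, and "retrieved data from discontinued subjects will be used to impute missing data for other discontinued subjects", using "an imputation model with only baseline effects (IGA as a factor" plus, for EASI75, baseline EASI.

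SAP 6.8.7 refers intercurrent events and missing values back to the protocol, so the rule in 14.3.7.1 stands.

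**The concern.** A model fitted only to data collected on IMP, and applied under MAR within arm, predicts what a discontinued subject would have scored had dosing continued. The stated estimand asks for the outcome whether or not dosing continued. One analysis therefore treats discontinuers in two ways: those who return contribute off-IMP values, and those who do not return contribute on-IMP predictions.

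The direction is not symmetric in principle. If stopping tralokinumab costs more than stopping placebo, the treatment difference is overstated in favour of tralokinumab. This is the primary analysis for two of the three key secondary endpoints. The trial has no formal testing (14.3.5) and exists to compare its estimates with the effect seen in LP0162-1339 (14.1), so each estimate should target the quantity it is said to estimate.

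**Working it through.** **Who is affected.** Only subjects who permanently stopped IMP, were not rescued, and have no Week 16 value.

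**Inputs from the documents.** About 50 subjects per arm (14.1). In the pooled AD trials, 2.3% of tralokinumab subjects permanently discontinued IMP because of adverse events (5.2). Inclusion criterion 11 equates 16 weeks with 5 half-lives. The documents give no all-cause discontinuation rate, SD, effect size or retrieval rate, so there is no figure of the plan's own to reproduce.

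**Assumed inputs.** Discontinuation 2.3% to 10%; half of discontinuers unrescued with no Week 16 value; off-IMP loss of 5, 10 or 15 SCORAD points in the tralokinumab arm and none in the placebo arm; SD 15 to 20.

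**Simple size.** Shift in the tralokinumab mean = (share discontinued × share missing) × loss.

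| Discontinued | Share affected | Subjects of 50 | Shift at loss 5 / 10 / 15 |
|---|---|---|---|
| 2.3% | 0.023 × 0.5 = 0.0115 | 0.6 | 0.06 / 0.12 / 0.17 |
| 5% | 0.05 × 0.5 = 0.025 | 1.25 | 0.13 / 0.25 / 0.38 |
| 10% | 0.10 × 0.5 = 0.05 | 2.5 | 0.25 / 0.50 / 0.75 |

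For scale, the 95% CI half-width is 1.96 × SD × √(2/50), which is 5.88 at SD 15 and 7.84 at SD 20. At a 10-point loss the shift is between 0.115/7.84 = 1.5% and 0.50/5.88 = 8.5% of that.

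**Allowing for washout.** The half-life is 16/5 = 3.2 weeks. At Week 16, 0.5^(8/3.2) = 18% of drug remains after a last dose at Week 8, and 0.5^(4/3.2) = 42% after Week 12. Late stoppers should therefore lose less.

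A simulation used 50 per arm, 1,500 runs, SD 15, correlation 0.85 per two weeks, placebo change −25, drug effect 5, 10 or 15 points decaying with this half-life after stopping at Weeks 4 to 12, half of discontinuers missing, and no rescue. Bias in the treatment difference (negative favours tralokinumab) was:

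| Discontinued | As planned, effect 5 / 10 / 15 | Copy-reference, effect 5 / 10 / 15 |
|---|---|---|
| 2.3% | −0.05 / −0.09 / −0.15 | −0.02 / −0.03 / −0.05 |
| 5% | −0.09 / −0.21 / −0.30 | −0.03 / −0.08 / −0.11 |
| 10% | −0.22 / −0.39 / −0.60 | −0.07 / −0.14 / −0.21 |

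The Monte Carlo standard error is 0.007 to 0.018. Copy-reference leaves about a third of the bias.

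**Wider assumptions.** With 5% to 15% discontinued, 80% to 0% of them retrieved, and a fixed loss of 6 to 12 points in the tralokinumab arm only, the overstatement runs from 0.05 × 0.2 × 6 = 0.06 to 0.15 × 1 × 12 = 1.8 points. Simulation agreed with these products within 0.05. If share and loss are equal in both arms, the net shift is zero.

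**DLQI visits.** Panel 2 schedules post-baseline DLQI at Weeks 2, 4, 8, 12 and 16, and 14.3.11 confirms Week 12 as the last assessment before Week 16. Section 14.3.7.1 nevertheless imputes at every second week, and 14.3.7.2 applies its SCORAD sequence, which includes Weeks 6, 10 and 14, to DLQI. No DLQI data are scheduled at those three visits to fit the models.

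**The case against.** The strongest reply is that the treatment of discontinuation is consistent, because retrieved values are used as observed. On this view MAR is a stated assumption about unobserved values, for perhaps one to three subjects per arm, and a tipping-point analysis tests it in the relevant arm. The reply continues that copy-reference swaps one untestable assumption for another, and that the size rests on invented inputs, with the direction built in by assuming no loss after stopping placebo. Early termination values are not later than the discontinuation date (SAP 6.8.2), so they can anchor the imputation. SAP 6.8.6 may also let an early termination or unscheduled visit on Days 106 to 119 stand in for Week 16. Finally, some failing discontinuers would be rescued and so leave the subgroup.

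Much of this stands. The subgroup is probably small, the inputs are assumed, and the direction depends on unequal losses. Retrieved data will often be too sparse for a separate model: the protocol expects small numbers, and SAP 6.6.1 already drops the primary-endpoint analysis if a group has too few data.

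Three things do not answer the point. MAR conditional on on-IMP data is not neutral for subjects known to have stopped, and the estimand says their off-IMP outcome counts. "The tipping point analysis will be performed using the missing at random imputed Week 16 data from primary analysis of the primary estimand", so its zero point is the on-IMP assumption. It also shifts every imputed tralokinumab value, including those of subjects who did not discontinue, and reports where the interval reaches zero without giving an estimate aligned with the estimand. Lastly, the anchoring and visit-window rules reduce the subgroup or its error but do not change the model applied to it.

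**Conclusion.** The concern holds. For unrescued discontinuers without a Week 16 value, the imputation in 14.3.7.1 follows a hypothetical strategy, while the estimand disregards discontinuation. The likely effect on SCORAD is small: about 0.05 to 0.15 points in favour of tralokinumab at 2.3% discontinuation and 0.22 to 0.60 at 10%, on the simulation's assumptions. It could reach 1.8 points in the extreme case of 15% discontinued, none retrieved and a 12-point loss. All of these rest on assumed loss, missingness and variability, and on no loss after stopping placebo. No size for DLQI can be derived from the documents. With no formal testing, this is a question of aligning estimate and estimand, worth correcting because it is cheap. The DLQI visit list is a separate wording error and adds nothing to the size of the main point.

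**What to change.** In the SAP, before the randomisation code is broken:

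1. Keep the within-arm MAR model, fitted to on-IMP and pre-rescue data, for subjects who did not discontinue but lack Week 16.
2. For discontinued, unrescued subjects without Week 16, impute from the placebo+TCS arm using the copy-reference steps in 14.3.7.2. For placebo discontinuers this is the same as within-arm imputation, and no drug effect is lost on stopping placebo. If enough discontinuers are retrieved, a baseline-only model fitted to those of the same arm, as in 14.3.6.2, is the alternative.
3. Report the present within-arm MAR analysis as a sensitivity analysis.
4. Report the number of subjects in this subgroup by arm.
5. State the DLQI imputation sequence as Weeks 2, 4, 8, 12 and 16 in both 14.3.7.1 and 14.3.7.2.

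The cost is SAP wording and restricting code already planned to one subgroup. The estimate may become slightly less favourable, the reference-based assumption cannot be tested, and on the simulation's assumptions about a third of the bias remains.

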14.3.7.2 Secondary estimand for the continuous key secondary endpoints: 'hypothetical'

The secondary estimand for the continuous secondary endpoints will be:

- Treatment difference in change from baseline to Week 16 in SCORAD and DLQI, respectively, if all subjects adhered to the treatment regimen in the sense that they did not discontinue IMP permanently and no rescue medication was made available before Week 16.

The secondary estimand assesses the expected benefit when adhering to the treatment regimen tralokinumab+TCS with no rescue medication as compared to a treatment regimen with placebo+TCS with no rescue medication.

Primary analysis for the secondary estimand - continuous key secondary endpoints

Data collected after permanent discontinuation of IMP or after initiation of rescue medication will not be included in the analysis. For subjects without any post-baseline data, the baseline value will be carried forward as the first post-baseline assessment, corresponding to imputing a change of 0 at the first post-baseline assessment. This is to ensure that all subjects will be included in the analysis. The endpoints will be analysed using a repeated measurements model on the post-baseline responses up to Week 16 with an unstructured covariance matrix, Kenward-Roger approximation to estimate denominator degrees of freedom, and the mean modelled as follows (shown for change from baseline in SCORAD):

Change from baseline in SCORAD

= treatment \times visit + baseline SCORAD \times visit + baseline IGA

This model assumes that data is missing at random within each treatment arm. The estimates will be presented with 95% CI at each visit. The primary comparison between tralokinumab+TCS and placebo+TCS will be at Week 16.

Sensitivity analysis for secondary estimand - continuous key secondary endpoints

Rather than assuming that observations are missing at random within each treatment arm it is assumed that missing data from subjects who discontinue IMP/receive rescue medication in the tralokinumab+TCS arm will resemble data from subjects from the placebo+TCS arm who do not discontinue IMP/receive rescue medication.

Imputation of missing data at Week 16 will be done using a pattern mixture model where missing data in the tralokinumab+TCS arm as well as the placebo+TCS arm will be imputed from the placebo+TCS arm (using multiple imputations in a so-called copy-reference approach).

The procedure for the change from baseline in SCORAD at Week 16 is described below. The same procedure will be applied for the DLQI endpoint.

1. Intermittent missing values will be imputed in each group using a Markov Chain Monte Carlo method to obtain a monotone missing data pattern and 100 copies of the dataset will be generated (seed=11101343).
2. For each of the 100 copies of the dataset, an ANCOVA model will be fitted to the SCORAD value at Week 2 in the placebo+TCS group. The model will include effects of baseline SCORAD as a covariate, and baseline disease severity (IGA 3 or 4) as factor. The estimated parameters, and their variances, will be used to impute missing values at Week 2 for the placebo+TCS group as well as the tralokinumab+TCS group (seed=16201343).
3. For each of the 100 copies of the dataset, missing values at Week 4 will be imputed in the same way as for Week 2. The imputations will be based on a similar ANCOVA model, but with SCORAD value at Week 2 included as an additional covariate. The parameters from the model will be estimated based on data from the placebo+TCS group. The estimated parameters, and their variances, will be used to impute missing values at Week 4 for both treatment groups.
4. This stepwise procedure will then be repeated sequentially for Weeks 6, 8, 10, 12, 14, and 16 with the SCORAD values from the preceding 2 visits included as covariates in addition to baseline SCORAD as a covariate, and baseline disease severity as factors.

For each of the 100 imputed datasets, the change from baseline in SCORAD at Week 16 will be analysed using an ANCOVA model with effects of treatment, baseline disease severity (IGA 3 or 4), and baseline SCORAD value. The estimated difference at Week 16 will be derived together with the associated standard error. The estimates and standard errors from the 100 analyses are pooled to one estimate and associated standard error using Rubin's rule to draw inference. From these pooled estimates, the 95% CI for the treatment difference will be calculated.

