14.1 Sample size

Approximately 100 subjects will be randomised 1:1 to tralokinumab+TCS or placebo+TCS to facilitate an evaluation of similarity with the treatment effect observed in the LP0162-1339 trial.

Randomisation will be stratified by baseline disease severity (IGA 3 or 4).

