14.3.8 Analysis of secondary endpoints

The analysis of the below dichotomous secondary endpoints will be based on the primary analyses of the primary estimand as specified above for the primary dichotomous endpoint.

For the continuous secondary endpoints, the analysis will be based on the primary (MMRM) analyses of the secondary estimand as specified above for the key secondary continuous endpoint.

The dichotomous secondary endpoints EASI90 at Week 16 and EASI50 at Week 16 will be analysed according to the primary analysis of the primary estimand as specified above for the primary endpoints.

The percentage change from baseline to Week 16 in EASI score and the change from baseline to Week 16 in Worst Daily Pruritus NRS weekly average, Eczema-related Sleep NRS (weekly average), and POEM will be analysed according to the primary (MMRM) analysis of the secondary estimand for the continuous key secondary endpoints.

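### Protocol 14.3.7.2: the hypothetical-estimand MMRM enters a fixed change of 0 as if observed for subjects with no post-baseline data, which fits neither its estimand nor its missing-at-random assumption (minor)

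*Protocol*

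**What the plan says.** Protocol 14.3.7.2 defines the secondary estimand for SCORAD and DLQI as the difference in change to Week 16 "if all subjects adhered to the treatment regimen in the sense that they did not discontinue IMP permanently" and with no rescue available before Week 16. Its main analysis is an MMRM on post-baseline responses with unstructured covariance. "Data collected after permanent discontinuation of IMP or after initiation of rescue medication will not be included in the analysis". For subjects with no post-baseline values, "the baseline value will be carried forward as the first post-baseline assessment, corresponding to imputing a change of 0 at the first post-baseline assessment". The reason given is: "This is to ensure that all subjects will be included in the analysis". The same section then says: "This model assumes that data is missing at random within each treatment arm". It also says: "The primary comparison between tralokinumab+TCS and placebo+TCS will be at Week 16".

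Protocol 14.3.8 extends the method. Percentage change in EASI and change in Worst Daily Pruritus NRS, Eczema-related Sleep NRS and POEM "will be analysed according to the primary (MMRM) analysis of the secondary estimand for the continuous key secondary endpoints". Protocol 14.3.11 takes the by-visit continuous estimates from the same model, and SAP 6.6.5 adds absolute change in EASI. SAP 6.8.7 refers missing values back to the protocol, so the rule stands unchanged.

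**The concern.** The estimand asks what would have happened under adherence without rescue, and the model answers by assuming that missing values follow the pattern of the subject's own arm. A fixed 0 at the first visit follows neither. Both arms may start daily TCS at Week 0, so a mean change of 0 at the first visit is implausible in either arm. The value also enters as an observation, with no allowance for its having been supplied by the analyst.

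The rule does not set Week 16 to 0. The zero enters at the first post-baseline assessment and reaches Week 16 through the covariance between visits. At stake are the first-visit estimates, which bear on onset of effect and take the shift in full, and to a lesser degree the Week 16 comparison. The size and sign depend on how many subjects in each arm have no data to contribute.

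**Working it through.** **What the plan supplies.** "Approximately 100 subjects will be randomised 1:1 to tralokinumab+TCS or placebo+TCS" (Protocol 14.1), so about 50 per arm. It states no mean change, SD, between-visit correlation or dropout rate, and there is no formal testing (Protocol 14.3.5). There is no figure of the plan's own to reproduce. All means, SDs and slopes below are assumptions.

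**Formula.** Let k of n subjects in an arm have the zero as their only value, let m be the arm's true mean change at the first visit, and let b be the within-arm slope of Week 16 on the first visit.

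- Shift in the arm mean at the first visit: (k/n)(0 − m).
- Shift in the arm mean at Week 16: b(k/n)(0 − m).
- Shift in the difference, tralokinumab minus placebo: the tralokinumab shift minus the placebo shift. The difference is negative when tralokinumab is better, so a positive shift dilutes it.

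**First assumed set.** SCORAD change at Week 2 of −20 vs −15 (difference −5) and at Week 16 of −39 vs −29 (difference −10). Equal SDs at eight visits with adjacent-visit correlation r give b = r^7: 0.32, 0.48 and 0.70 for r = 0.85, 0.90 and 0.95.

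- One placebo subject, Week 2: −(1/50)(15) = −0.30, and 0.30/5 = 6% inflation. Week 16: 0.32 × 0.30 = 0.10 to 0.70 × 0.30 = 0.21, or 1.0 to 2.1% of 10.
- One tralokinumab subject, Week 2: (1/50)(20) = +0.40, and 0.40/5 = 8% dilution. Week 16: 0.32 × 0.40 = 0.13 to 0.70 × 0.40 = 0.28, or 1.3 to 2.8%.
- Two placebo subjects and none on tralokinumab, r = 0.90: Week 2 is −5 − 0.60 = −5.60; Week 16 is −10 − 0.478 × 0.60 = −10.29.
- Three tralokinumab subjects and none on placebo, r = 0.90: Week 2 is −5 + 1.20 = −3.80; Week 16 is −10 + 0.478 × 1.20 = −9.43.

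**Second assumed set, by simulation.** Week 2 means −18 vs −14, Week 16 difference −11, b = 0.80, eight visits, 50 per arm, unstructured covariance fitted by maximum likelihood, 200 replicates per scenario. Each data set was fitted with and without the zeros. The SD of the Week 16 estimate was about 3.3 to 3.8.

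| Affected (tralokinumab, placebo) | Formula shift, Week 16 | Simulated shift, Week 16 | Shift / SD |
|---|---|---|---|
| (1, 1) | +0.06 | +0.07 | 2% |
| (3, 3) | +0.19 | +0.21 | 6% |
| (1, 0) | +0.29 | +0.29 | 8% |
| (0, 1) | −0.22 | −0.23 | 6% |
| (3, 0) | +0.87 | +0.87 | 27% |
| (0, 3) | −0.67 | −0.67 | 20% |
| (5, 0) | +1.44 | +1.46 | 41% |
| (0, 5) | −1.12 | −1.11 | 31% |

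Formula and simulation agree. One subject in one arm is 0.22/11 = 2.0% to 0.29/11 = 2.6% at Week 16. At Week 2 it is (14/50)/4 = 7% to (18/50)/4 = 9%, so the first-visit percentage depends on the assumed early difference. Without the zeros the simulated Week 16 differences were −10.7 to −11.3, consistent with −11.

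**Wider range.** For a first-visit change of −8 to −25 and b of 0.4 to 1.0, one affected subject moves its arm's Week 16 mean by 0.4 × 8/50 = 0.06 to 1.0 × 25/50 = 0.50 points.

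**The plan's own alternatives.** Protocol 14.3.7.1 handles missing values in unrescued subjects by sequential multiple imputation starting at Week 2. The copy-reference analysis in 14.3.7.2 imputes missing Week 2 values from a model. Neither uses a zero.

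**The case against.** The strongest reply is that few subjects will be affected. Protocol 9.5 asks for assessments just before rescue, at an unscheduled visit if necessary. Protocol 14.3.4 treats an assessment on the day rescue starts as uninfluenced. Protocol 14.3.6 dates discontinuation at the early termination visit for withdrawn subjects, so data up to that visit are kept. SAP 6.8.6 lets early termination or unscheduled data from Day 8 to 21 stand in for a missing Week 2 visit. The supplied TCS is not rescue. The rule's wording also refers to having no post-baseline data at all; extending it to subjects with none left after the exclusions is the natural reading, given the preceding sentence and the stated aim, but it is not spelled out. All of this stands and limits the size. It does not make 0 the right value.

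A reader might infer that the rule biases the result in tralokinumab's favour. The documents do not support that: they give no counts by arm, the direction can go either way, and balanced counts leave little. A reader might also infer that EASI, itch and POEM have no other analysis. They do. EASI50/75/90, the itch reduction of at least 4 and, through SAP 6.6.4, the POEM reduction of at least 4 are analysed as responders under the composite estimand. For SCORAD and DLQI, the primary (composite) analysis does not use the rule.

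The remaining objection is that deleting the rule drops subjects from a full-analysis-set analysis. This carries little weight. Under missing at random, a subject with no post-baseline outcome holds essentially no information on the change. Nor is full inclusion held to elsewhere: SAP 6.8.1 excludes subjects with no baseline value from change-from-baseline analyses.

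**Conclusion.** The inconsistency is established from Protocol 14.3.7.2 alone: the fixed 0 matches neither the stated estimand nor the stated missing-data assumption. Its numerical effect is conditional and probably small. Under the assumed values with 50 per arm, one affected subject moves the Week 16 difference by about 1 to 3%, and the first-visit difference by 6 to 8% in the first set (7 to 9% in the second). Three in one arm and none in the other move Week 16 by about 3 to 8%. With none affected the effect is nil.

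The rule matters most for percentage change in EASI, pruritus NRS, sleep NRS and POEM, where this MMRM is the only planned model of the continuous change, and for the by-visit estimates. The copy-reference analysis covers SCORAD and DLQI only. It also changes the missing-data assumption, so it cannot isolate the effect of the zero. In a trial that estimates without formal testing, and for a rule outside the primary estimand, the point is minor.

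**What to change.** Delete the baseline-carried-forward sentence from 14.3.7.2, through an SAP update as Protocol 14.3.16 permits. Fit the MMRM to observed on-treatment, rescue-free post-baseline data. Report, by arm and endpoint, the number of full-analysis-set subjects who contribute no outcome. If those subjects are missing at random given baseline, the shift disappears.

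If every full-analysis-set subject must appear, impute their post-baseline values by multiple imputation from baseline, within arm and under missing at random, with post-rescue and post-discontinuation values treated as missing. The procedure in 14.3.7.1 cannot be borrowed as it stands, because it imputes only unrescued subjects and gives rescued ones their worst observation carried forward.

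The first option costs one deleted sentence and one line of reporting; its downside is that a few subjects may contribute no outcome to this MMRM. The second needs its imputation model written out and, under the same assumption, adds essentially no information.
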